Increased incidence and life expectancy has resulted in a growing population of metastatic breast cancer (MBC) patients.¹ MBC patients have poorer quality of life (QOL) and higher rates of functional decline and premature mortality compared to early stage survivors and healthy controls.²⁻⁴ Interventions are needed to alleviate adverse health effects and allow metastatic patients to function optimally in the years they survive with advanced cancer. However, few health-enhancing interventions exist for women with MBC. Increased physical activity (PA) is consistently associated with fewer treatment-related side effects, higher QOL, increased survival and reduced recurrence and mortality among early stage survivors.⁶⁻⁹ Increasing light intensity PA and reducing time spent sedentary may also reduce functional decline,¹⁰ improve QOL and QOL^{11, 12} and body composition¹³ and reduced mortality¹⁴ independent of more intense PA. However, there is a paucity of research on PA in MBC patients, and existing interventions have been deemed not feasible due to their focus on intense PA and/or requiring on-site visits. mHealth PA interventions may be particularly useful for these women because they allow for remote monitoring of patients which facilitates individual tailoring of PA programs to patient's abilities and do not require travel to on-site, supervised PA sessions, reducing participant burden. Yet, no studies have examined a mHealth PA intervention in MBC patients. We propose to address these critical research gaps by testing a highly tailored technology-supported intervention to promote PA of any intensity (i.e. light, moderate or vigorous) via increasing daily steps in MBC patients. This approach may have substantial health benefits for MBC patients, facilitate gradual and safe adoption of more intense PA and be more achievable than high volumes of more strenuous PA.^{17, 18} The primary aim of this study is to pilot test the feasibility and acceptability of a 12 week technology-supported intervention to increase PA in inactive MBC patients (n=50) using a two-arm randomized control trial (*Fit2ThriveMB* versus education control). The *Fit2ThriveMB* intervention consists of a Fitbit, coaching calls and the *Fit2ThriveMB* smartphone app which provides self-monitoring, a tailored goal-setting tool, real-time tailored feedback, app notifications, and a group message board. We will also examine outcome patterns suggesting the efficacy of *Fit2ThriveMB* on symptom burden, QOL and functional performance, important outcomes in MBC patients compared to the education control. The primary outcome time point is post-intervention 12 weeks. This project is significant because it will provide essential evidence to support the feasibility, acceptability and health benefits of increasing PA in MBC patients using a scalable intervention strategy that could be easily integrated into care to improve health and disease outcomes in this population.

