
3.0 Inclusion and Exclusion Criteria:

Inclusion criteria:

- Female; ≥ 18 years of age
- Diagnosed with metastatic breast cancer or locally advanced disease not amenable to surgical resection (Metastases to the auxiliary lymph nodes, and nowhere else in the body, do not qualify).
- Fluent in spoken and written English
- Own a smartphone
- Have access to the internet to complete assessments

- Self-report engaging in <150 minutes of moderate to vigorous PA per week.

Exclusion criteria:

- Untreated brain metastases
- Breast cancer with metastases to only the auxiliary lymph nodes.
- Uncontrolled cardiovascular disease or other major contraindications (i.e. non-ambulatory, severe cognitive or functional limitations) to PA participation
- Current enrollment in another dietary or PA trial

All MBC patients must obtain medical clearance from their oncologist to participate.

Adults unable to consent/Cognitively Impaired, individuals who are not yet adults (under 18 years of age), pregnant women and prisoners or other detained individuals will NOT be included in the present study.

4.0 Sample Size:

We will recruit 50 metastatic breast cancer patients to participate in this study. Sample size calculations (n=50) are based on the successful completion rate defined as: a) an attrition rate of $\leq 20\%$ (i.e. complete 12 week assessment) and b) adherence to daily goals and wearing Fitbit $\geq 70\%$ of study days (i.e. $\sim 59/84$ days). With half of participants (n=25) assigned to each condition, there is $>85\%$ power to differentiate between a 60% (control) and 80% (*Fit2ThriveMB*) “successful completion” rate with a one-tailed, exact test for binomial proportion at a 0.05 significance level (SAS V9.4).

5.0 Recruitment and Screening Methods:

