| Social Support Exercise (SSE) | X | X | X |
| Sitting Time Questionnaire (STQ) | X | X | X |
| Process Evaluation | | | X |
| COVID-19 Assessment | X | X | X |
| Weight | X | | X |
| Blood Pressure | X | | X |
| SPPB | X | | X |
| Senior Fitness Test | X | | X |
| 6 minute Walk | X | | X |

Data quality control/checking

The majority of data is collected (PA, symptoms, acceptability) or uploaded electronically. The quality of these data will be checked by examining descriptive statistics and score ranges of all variables for missing and/or erroneous values. All data will be examined for violation of basic statistical assumptions (i.e. normality, multicollinearity) and transformed, if needed. Participants will be asked to complete all assessments, regardless of group assignment or adherence. Strategies for handling missing data (i.e. maximum likelihood estimation, multiple imputation) will be chosen based on the type and extent of the problem.

Statistical Analyses Plan

Aim 1. Feasibility and acceptability will be analyzed using descriptive statistics (frequencies, means and standard deviations). Feasibility will primarily be evaluated using the “successful completion rate” defined as: a) $\geq 80\%$ of MBC patients who enroll in the intervention will remain in the intervention and b) MBC patients will adhere to daily goals and wear Fitbit $\geq 70\%$ of study days (i.e. $\sim 59/84$ days) If a successful completion rate is achieved, *Fit2ThriveMB* will be deemed feasible. Additional measures of feasibility, fidelity, acceptability and safety will also be summarized and considered with the “successful completion” rate before proceeding with a more definitive trial.

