Aim 2 and Exploratory Aim. We will employ an intent-to-treat (ITT) approach by including all participants recruited into the study regardless of compliance. Every effort will be made to collect all outcome measures even if a participant does not engage in assigned treatments. Analysis of covariance (ANCOVA) will be used to compare study groups with respect to mean changes in each outcome from baseline to 12 weeks with baseline adjustment. Data from these analyses will provide estimated means, standard errors, and preliminary effect sizes for the *Fit2ThriveMB* intervention. These data will be used for future sample size calculations, to identify a primary endpoint and further refine the *Fit2ThriveMB* intervention to be tested in a more definitive trial. We will also use regression models to explore the relationship between changes in each outcome and intervention adherence. This study is not designed to make conclusions about *Fit2ThriveMB* efficacy without further study.

Timeline

The overall duration of the study will be 2 years, and each participant will be actively participating for 12 weeks.

10.0 Research with Vulnerable Populations:

Non-English Speaking Subjects: N/A

Subjects who are not yet adults (infants, children, teenagers): N/A

Cognitively Impaired Adults: N/A

Adults Unable to Consent: N/A

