In addition to the potential minimal risk associated with PA participation and remote functional performance testing, there are some potential minimal psychological risks associated with answering some of the questionnaires required for participation in this study. However, participants will be given the option to skip any questions that make them feel uncomfortable. Should any individuals report scores on the PROMIS Cancer Depression Scale, that are in the 75th percentile (i.e. ≥ 4.3) or confer a high level of distress in interactions with research study staff, they will be referred to the Supportive Oncology program at Northwestern: <https://www.cancer.northwestern.edu/cancer-care/patient-support/index.html>.

There may also be a security risk in using Zoom video conference software to communicate with participants during remote functional performance testing and orientation sessions. In order to minimize the risk of using Zoom video conference software and enhance security, all participants will be sent individual links to attend the

video conference to their email with a password that will be required to enter the meeting. Study staff will also enable the ‘waiting room’ feature on Zoom so that only members permitted by the meeting host (study staff member) will present in the video conference.

There is also a small risk to individuals’ privacy when using the mHealth app but this will be minimized by the procedures described, above.

Participants are permitted to refuse to participate in any aspect of the research and may withdraw from the study at any point, for any reason without penalty. For any participant who elects to withdraw, permission will be sought to continue to collect outcome data for use in the analysis. However, all participants in the intervention will be accounted for in all follow-up analyses following the intent-to-treat principle. If participants withdraw from the study, and do not agree to return for follow-up assessments, data from their most recent assessment will be carried forward and imputed in subsequent assessment points (Last Observation Carried Forward).

Protection against Risk

The following procedures will be used to minimize risk:

- Numerous studies have demonstrated that physical activity is safe, feasible, and beneficial for cancer patients and survivors, including those with advanced disease.
- Potential participants will be screened using a standard tool to assess readiness to engage in physical activity.

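### Section 19.0 prescribes LOCF for women who refuse follow-up, section 9.0 leaves other methods open, and with outcomes only at weeks 0 and 12 LOCF enters zero change as if observed

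*Combined protocol and SAP*

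**What the plan says.** Two sections give rules for missing outcomes.

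- **Section 19.0, withdrawal paragraph.** For any woman who withdraws, "permission will be sought to continue to collect outcome data for use in the analysis". If she also declines follow-up, "data from their most recent assessment will be carried forward and imputed in subsequent assessment points (Last Observation Carried Forward".
- **Section 9.0, Data quality control/checking.** "Strategies for handling missing data (i.e. maximum likelihood estimation, multiple imputation) will be chosen based on the type and extent of the problem". LOCF is not among the methods named.

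The Statistical Analyses Plan in section 9.0 (Aim 2 and Exploratory Aim) states that "Analysis of covariance (ANCOVA) will be used to compare study groups with respect to mean changes in each outcome from baseline to 12 weeks", adjusted for baseline, under an intent-to-treat approach "including all participants recruited into the study regardless of compliance". It names no missing-data method. On the use of the results it says: "These data will be used for future sample size calculations, to identify a primary endpoint".

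The outcomes named in Aims 2 and 3 have two time points. The Assessments text puts accelerometry and functional testing at baseline and 12 weeks. Table 4 lists the PROMIS symptom and function scales, FACT-B, SPPB, Senior Fitness Test and 6-minute walk at w0 and w12 only. Women are randomised after their baseline data are verified. The sitting-time questionnaire and several social-cognitive scales also have a week-3 value, and the point does not extend to them.

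**The concern.** With one value before randomisation and one at week 12, the last observation for a woman who refuses follow-up is her baseline value. LOCF therefore gives her a change of exactly zero, and the ANCOVA treats it as measured.

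Two things follow. Identical zeros carry no spread of their own, so the residual variance usually comes out too low. And the estimated effect is right only if withdrawers truly end where they began, or if their departures from that happen to balance between arms. No analysis tests this. It is doubtful for symptoms and function in a population that section 2.0 describes as having "higher rates of functional decline and premature mortality compared to early stage survivors and healthy controls".

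Effect and residual variance are the two inputs to the sample size of the next trial. In addition, because two rules stand unranked and one of them is open, the method can be settled after the data are seen.

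**Working it through.** The plan gives no figure of its own on this point, so there is none to reproduce.

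**Inputs from the documents.** 25 women per arm and an attrition limit of 20% (section 4.0, where retention means "i.e. complete 12 week assessment"); ANCOVA of change on arm and baseline (section 9.0). The limit is 0.20 × 25 = 5 women per arm. Counting all of them as refusals makes this an upper value.

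**Assumptions not in the documents.** SD 1 at both visits; completers' true difference 0.50 SD with control completers unchanged; correlation r between visits of 0.5 to 0.7; 2 (8%) or 5 (20%) refusals per arm; and three versions of what withdrawers truly do:
- A: they keep their arm's mean change.
- B: they lose the benefit and end at baseline.
- C: they worsen by 0.5 SD, with 5 intervention and 2 control refusals.

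**Step 1, effect.** Let d be the share withdrawn and m the withdrawers' true mean change (1 = intervention, 0 = control; higher is better). Then LOCF effect − ITT effect = d0·m0 − d1·m1. With 5 intervention refusals:
- A: 0.20 × 0 − 0.20 × 0.50 = −0.10
- B: 0
- C: 0.08 × (−0.5) − 0.20 × (−0.5) = +0.06

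**Step 2, residual variance.** In case A with equal d, the ratio of LOCF to full data is (1−d)·[1 + d(1−r)/(1+r) + d·M/(1−r²)], where M is the average over arms of the squared mean change: (0 + 0.25)/2 = 0.125.
- d = 0.20, r = 0.5: 0.80 × (1 + 0.067 + 0.033) = 0.88
- d = 0.20, r = 0.7: 0.80 × (1 + 0.035 + 0.049) = 0.87
- d = 0.08, r = 0.5: 0.92 × (1 + 0.027 + 0.013) = 0.957
- d = 0.08, r = 0.7: 0.92 × (1 + 0.014 + 0.020) = 0.951

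The direction is not fixed. At d = 0.20 the ratio passes 1 once the root-mean-square arm change exceeds about 0.83 SD (r = 0.5) or 0.74 SD (r = 0.7). In a simulation with arm changes of −1.2 and −0.7 SD at r = 0.7, the variance rose from 0.51 to 0.59.

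**Step 3, next-trial sample size.** n is proportional to residual variance / effect². Case A, 5 per arm, r = 0.5: 0.88 × (0.50/0.40)² = 1.375.

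Simulation (20,000 trials per scenario, r = 0.5, 0.6, 0.7) agrees. Variance and n are ratios of LOCF to full data:

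| Case | Refusals | ITT effect | LOCF | Available-case | Variance ratio | n ratio |
|---|---|---|---|---|---|---|
| A | 2 v 2 | 0.50 | 0.46 | 0.50 | 0.95-0.96 | 1.12-1.13 |
| A | 5 v 5 | 0.50 | 0.40 | 0.50 | 0.87-0.88 | 1.36-1.38 |
| B | 2 v 2 | 0.46 | 0.46 | 0.50 | 0.93-0.95 | 0.93-0.95 |
| B | 5 v 5 | 0.40 | 0.40 | 0.50 | 0.83-0.86 | 0.83-0.86 |
| C | 5 v 2 | 0.34 | 0.40 | 0.50 | 0.78-0.82 | 0.56-0.60 |

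The available-case n ratio is 0.83-0.84 (2 per arm) and 0.61-0.63 (5 per arm) in B, and about 0.39-0.41 in C.

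**Step 4, drawn values.** Return to baseline by multiple imputation (case B, 5 per arm, r = 0.5) gives the same effect as LOCF, 0.401. Its residual variance is 0.776, against 0.766 with full data and 0.657 under LOCF. Drawing values repairs the variance; the assumption about the mean remains.

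**Step 5, scale.** The LOCF standard error is 0.19-0.24 SD. With 50 women and three fitted parameters, the sampling coefficient of variation of the residual variance is √(2/47) = 0.21.

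**The case against.** **The rules may be complementary.** Section 19.0 is specific (withdrawn and refusing), section 9.0 is general, and a specific rule normally governs its own case. A reader might infer a flat contradiction; the documents do not go that far. But no text states this division, and on this reading LOCF still governs exactly the women for whom it enters zeros.

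**LOCF is not the worst estimator of the effect.** This stands. With 5 intervention refusals and r = 0.5, root-mean-square error against the ITT effect is lower for LOCF than for available-case ANCOVA: 0.247 v 0.274 in A, 0.230 v 0.296 in B, 0.241 v 0.308 in C. A reader might infer that the analysis should simply switch to women with week-12 data. The figures do not support that, and dropping the other women sits badly with the plan's intent-to-treat wording.

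**The sizes rest on outside assumptions.** Also true. Section 2.0 compares rates of decline with other groups and gives no 12-week figure, so it does not establish the decline in case C. Section 19.0 seeks outcome data after withdrawal, so refusals may be well below 5 per arm.

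**This is a pilot.** Section 9.0 disclaims conclusions about efficacy. That limits severity, but the disclaimer does not cover the stated use of the estimates for planning.

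**Conclusion.** The point holds at low severity: it should be fixed, on secondary estimates only. A stated rule enters exact zeros as observed data, another section leaves the method open, and no sensitivity analysis is planned. Under the assumptions above, the residual variance is 4-7% too low with 2 refusals per arm and 12-17% too low with 5 (cases A and B). The effect may be too small (A), right (B) or too large (C). A next-trial sample size built on LOCF could be 36-38% too large or 40-44% too small at the extremes, and 12-13% too large to 5-7% too small with 2 refusals per arm.

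Three stronger readings are not supported:
- That LOCF always lowers the variance. It reverses when arm mean changes are large.
- That the LOCF standard error is wrong for its own estimator. It matches the sampling SD (0.231 v 0.226 with 5 per arm, r = 0.5).
- That LOCF creates false positives. With no true effect, a shared decline of 0.2-0.5 SD and 5 v 2 refusals, the spurious effect is 0.02-0.06 SD and the false-positive rate stays at 5.0-5.6%.

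Aim 1 is unaffected, and the effect distortions of at most 0.10 SD are smaller than the pilot's standard error.

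**What to change.** Delete the LOCF sentence in section 19.0 and refer to section 9.0. In section 9.0, replace the open choice with one pre-specified rule for all Aim 2 and 3 outcomes. It should use maximum likelihood or multiple imputation with drawn values, not single carried-forward values, and keep every randomised woman in her assigned arm.

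The sponsor chooses whether the primary assumption is missing at random or return to baseline, since neither is best in every case. With two time points and no auxiliary data, likelihood under missing at random gives the same answer as available-case ANCOVA. If that is chosen, the text should say that women without week-12 data enter through the sensitivity analyses.

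Pre-specify as sensitivity analyses:
1. The assumption not chosen as primary.
2. Unfavourable shifts for withdrawn women, for example 0.2 and 0.5 SD in each scale's own direction, once in both arms and once in the intervention arm only. With 5 refusals per arm, a 0.5 SD shift in both arms cancels; in the intervention arm alone it moves the effect from 0.50 to 0.40 (0.20 × 0.5 = 0.10).

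Compute the next-trial sample size under both primary assumptions.

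**Cost.** A few sentences, slightly more programming, and a standard error larger than under LOCF by about 7% with 2 refusals per arm (1/0.938) and 20% with 5 (1/0.837). Under return-to-baseline imputation, the usual combining rules are conservative: 0.276 against a sampling SD of 0.225 (5 per arm, r = 0.5).

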This study is classified as minimal risk because the probability and magnitude of harm or discomfort anticipated is not greater than those ordinarily encountered in daily life or during the performance of routine physical and psychological examinations or tests and confidentiality is adequately protected. The PI and study investigators will conduct continuous review of data and patient safety. Any staff member or investigator can spontaneously identify an adverse event. Participants will be instructed to call or e-mail the PI in the event of any emergencies or medical events within 24 hours of the event occurring. These instructions will be included in all cover letters that accompany study materials and displayed prominently within the app.

Events may also be spontaneously reported to staff during contact time. Adverse events and serious adverse events may also be identified during regularly scheduled calls or emails by researchers blinded to the treatment condition of the participant. These phone interviews or emails will be conducted every 4 weeks throughout the

12 week study period. Participants will be asked to complete the Non-spontaneous Adverse Events Questionnaire either via REDCap or via an interview with study staff. This form will be completed for all metastatic breast cancer survivor participants and will query the participant as to whether they have had any health and/or medical problems during the preceding 4 week period. Participants will be called or emailed until a response is received. Participants will also be required to provide the investigators with at least one emergency contact to have on file in the event we are fail to reach the participant after 5 or more attempts. If participant reports “YES” to item 5A-5D (see REDCap form), an adverse event form will be filed with the IRB.

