All identified adverse events will be reported to the PI and recorded and reported in an adverse event log (includes subject’s name, date and event description). The PI will consult with co-investigators, the IRB and NU Office for the Protection of Research Subjects to determine whether the event should be classified as ‘non-attributable’, ‘possibly attributable’ or ‘attributable’ to the current project and ‘serious’ or ‘non-serious.’ Adverse event reports will be submitted to the IRB within 5 business days of the event or notification to the PI that the event has occurred. All serious adverse events will be reported to the RHLCCC Clinical Research Office for review by the Data Monitoring Committee, IRB, and the National Cancer Institute, as applicable, using appropriate forms. Any action to be taken will be recorded in the adverse event log.

An adverse events is defined as an unanticipated problem which meets all of the following criteria: a) unexpected (in terms of nature, severity, or frequency) given the research procedures described in protocol-related documents and the characteristics of the subject population being studied, b) related or possibly related to participation in the research and c) suggests that the research places subjects or others at a different or greater risk of harm than was previously known or recognized. A ‘serious’ adverse event is defined as any event in which the outcome results in any of the following: death, a life-threatening adverse drug experience, inpatient hospitalization or prolongation of existing hospitalization (for > 24 hours), a persistent or significant disability/incapacity or substantial disruption of the ability to conduct normal life functions; a congenital anomaly or birth defect; important medical events that may not result in death, be life threatening, or require hospitalization may be considered a serious adverse drug experience when, based upon medical judgment, they may jeopardize the participant and may require medical or surgical intervention to prevent one of the outcomes listed, above. All other events will be considered ‘non-serious.’

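### Section 21.0 defines an adverse event by the criteria for an unanticipated problem, so expected non-serious harms fall outside the log and semi-annual reports as written, and the position of unrelated events is contradictory

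*Combined protocol and SAP*

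**What the plan says.** All of the defining text is in section 21.0 (Data Monitoring Plan to Ensure the Safety of Participants).

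- **Definition.** "An adverse events is defined as an unanticipated problem which meets all of the following criteria". The event must be (a) unexpected in nature, severity or frequency, (b) "related or possibly related to participation in the research", and (c) suggestive of a risk different from or greater than the one already recognised. No other section gives a wider definition.
- **Serious events.** These are defined by outcome: a serious "adverse event is defined as any event in which the outcome results in any of the following", followed by a list of outcomes. The next sentence places every remaining event in the non-serious class.
- **Log and workflow.** "All identified adverse events will be reported to the PI and recorded and reported in an adverse event log". The PI, with others, then determines whether the event "should be classified as ‘non-attributable’, ‘possibly attributable’ or ‘attributable’ to the current project", and whether it is serious.
- **Collection.** Every 4 weeks all participants are asked "whether they have had any health and/or medical problems during the preceding 4 week period". They are also told to contact the PI "in the event of any emergencies or medical events within 24 hours of the event occurring". A YES to questionnaire items 5A-5D leads to an adverse event form being filed with the IRB.
- **Reporting.** "Adverse event reports will be submitted to the IRB within 5 business days of the event", or of the PI being notified. Non-serious adverse events go to the cancer center's Clinical Research Office twice a year, and the semi-annual progress reports to its Data Monitoring Committee include reported adverse events. One clause also refers, in general terms, to telling the IRB about events as they happen.

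Section 19.0 names the foreseen harms: sore muscles, strains and worsened arthritis from increasing activity, and strains, falls or injuries during remote functional testing. The Statistical Analyses Plan in section 9.0 (Aim 1) says that safety will be summarised and weighed before a more definitive trial.

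**The concern.** The three criteria describe an unanticipated problem, which is the label the protocol itself gives them. That is a narrow subset of harms. Here the subset has become the definition of the whole category, and the duties to log and to report semi-annually are tied to the category's name.

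The harms most clearly left out are those the protocol expects increased activity to cause. For an activity intervention in inactive women with metastatic disease, the frequency of those harms is what the next trial's planners will want to know. If the safety summary is drawn from the log or the semi-annual reports, a low count could mean few harms or could simply reflect the definition, and a reader could not tell which. Staff who follow the definition and staff who follow the attribution workflow could also log different events.

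**Working it through.** No arithmetic applies: the plan gives no adverse event rate, and the documents offer no basis for estimating how many events would be left out. The check applies the definition to each kind of event and then asks whether other text restores what it excludes.

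**Applying the definition as written**

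1. *Non-serious, related, and of expected nature, severity and frequency* (for example, the soreness or strains foreseen in section 19.0). It fails criterion (a). As a recognised risk it ordinarily fails (c) too. It is not an adverse event.
2. *Non-serious, unexpected, unrelated.* It fails criterion (b). By the definition it is not an adverse event.
3. *Non-serious, unexpected, at least possibly related, and pointing to new or greater risk.* It meets all three criteria and is an adverse event.
4. *Any event with a listed serious outcome.* The serious definition turns on outcome alone and repeats none of the three criteria.

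**Following the duties.** The log covers identified adverse events. The semi-annual submission covers non-serious adverse events, and the committee's reports list reported adverse events. Each duty uses the defined term, so case 1 falls outside all of them.

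**Does other text restore case 1?**

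- The 4-weekly questionnaire and the 24-hour instruction govern what is collected. Neither says that a collected event enters the log or counts as an adverse event.
- The 5A-5D rule depends on the participant's answer, not on criteria (a) to (c), so it may bring in some case 1 events. The item wording is not in the documents, and filing a form with the IRB is not stated to be entry in the log.
- The clause about telling the IRB of events as they happen does not mention the log or the committee's reports.

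None of these clearly restores case 1.

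**Does other text restore case 2?** Here the section points both ways. Criterion (b) excludes the event. The non-attributable class implies that events are logged first and attributed afterwards, and the sentence placing all remaining events in the non-serious class points the same way. This is an internal conflict, not a settled exclusion.

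**The case against.** The strongest reply is that section 21.0, read as a whole, was meant to capture widely. It asks every participant about any health problem, requires an adverse event form on certain answers whatever the expectedness or relatedness, has a class for non-attributable events, and sorts all events into serious and non-serious. It could be added that the Aim 1 safety summary is not expressly confined to the log, so questionnaire data could feed it.

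Much of this stands. It defeats two stronger readings that a reader might infer:

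- *That expected or unrelated harms go uncollected or unreported altogether.* The documents do not support this. The questionnaire and the 24-hour instruction reach such events, and the 5A-5D rule may carry some of them to the IRB.
- *That unrelated non-serious events are definitely excluded.* The attribution classes suggest otherwise, so only a conflict can be claimed.

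What does not stand is the conclusion that no change is needed. Evidence of a wider intention does not override an explicit requirement that all three criteria be met, and nothing expressly returns expected non-serious harms to the log. That the Aim 1 text does not name its source of safety data leaves the question open; it does not settle it.

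**Conclusion.** The point holds for expected non-serious harms: as written, they are outside the adverse event log and the semi-annual reports. For non-serious unrelated events, the finding is that section 21.0 contradicts itself and must be reconciled.

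A reader might also infer that serious events are lost when they are expected or unrelated. The documents do not support treating that as a finding, because the serious definition is framed by outcome and carries none of the three criteria.

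The size cannot be stated as a number of events. The consequence is limited: safety is an additional descriptive measure without a threshold, and the primary outcome (feasibility and acceptability) does not depend on it. The point still merits correction because safety is considered before a more definitive trial. The conclusion assumes that staff apply the definition as written and that the unseen questionnaire items 5A-5D do not themselves require entry in the log. If they do, some of the gap closes in practice, but the text would still need to say so.

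**What to change.** In section 21.0:

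1. Define an adverse event as any untoward medical occurrence from consent to the week-12 assessment, whether or not it is expected or related. Symptoms already present at consent are logged only if new or worse.
2. Keep criteria (a) to (c) solely as the definition of an unanticipated problem.
3. Record expectedness, attribution and seriousness after each event is logged.
4. Reconcile the 5-business-day IRB sentence, the 5A-5D filing rule and the general clause on telling the IRB of events with these terms. The wider definition should not by itself send every logged event to the IRB within 5 business days.

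The cost is protocol wording, more rows in the log and longer semi-annual reports. The change in IRB workload depends on how step 4 is written, so that step should be made together with the first.
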